4.6 Subject Withdrawal

Subjects (or their legal surrogates if subjects become unable to make informed decisions) can terminate study participation at any time without prejudice. If a subject terminates participation before completing the study, the reason for this decision will be recorded in the electronic case report form (eCRF).

Subjects who indicate interest in withdrawing from the study should also be asked permission to be contacted at Day 28 by telephone for vital status (any AEs that occurred during the study). This is not considered full withdrawal of consent, but the modified consent for limited follow-up should be noted in the medical record.

Subjects who fully withdraw consent will not be contacted further.

Subjects who withdraw from the study will not be replaced.

4.7 Discontinuation of Study Medication

The investigator will instruct subjects to stop study medication for any of the following reasons:

- The investigator becomes aware that the subject has renal insufficiency
- Any other AE for which the investigator believes that continuation of the study medication would be detrimental to the subject
- Subject is found to be pregnant
- Subject is hospitalized within 5 days of enrollment

The reason for discontinuation of the study agent is to be recorded in the source documentation and on the eCRF. All subjects who discontinue study drug will be encouraged to comply with the

study visit schedule including clinical and virologic assessment. In any event, AEs that lead to stopping study medication will be followed until resolution or stabilization if possible.

4.8 Discontinuation of Subject by Investigator

The investigator has the right to withdraw subjects from the study. Subjects may be withdrawn from the study for any of the following reasons:

- The subject is lost to follow-up
- The subject experiences an AE, and the investigator believes that continuation in the study would be detrimental to the subject (in contrast to discontinuing the study medication and continuing follow-up as discussed in Section 4.7)
- Subject is hospitalized within 5 days of enrollment

The reason for withdrawal from the study is to be recorded on the eCRF. If a non-serious AE is unresolved at the time of discontinuation, efforts should be made to follow-up until the event resolves or stabilizes, the subject is lost to follow-up, or there is some other resolution of the event. The investigator is to make every attempt to follow all serious adverse events (SAEs) to resolution.

Subjects who miss a study visit should be contacted to reschedule. If subjects cannot be contacted immediately, periodic attempts should continue until study completion (Study Day 28 \pm 3). Lost to follow-up is defined as unsuccessful contact after at least 3 documented telephone calls.

Any subject withdrawn from the study will not be replaced.

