3.2 Definitions for the Purpose of this Study

Enrolled

For the purpose of collecting data and samples, and reporting AEs, a subject will be considered enrolled beginning from the time the informed consent form is signed until the subject is considered “screen failure,” “discontinued,” or “completed.”

Randomized

Subjects are considered randomized when they meet all of the following criteria:

- Confirmation that the inclusion and exclusion criteria are met
- Consent is given and signed by the subject for the study
- Randomization number is assigned

Screen Failures

Subjects are considered screen failures when they meet one of the following criteria after signing consent:

- Screening tests reveal that the subject is ineligible
- Subject withdraws consent before being randomized

Discontinued

Subjects are considered discontinued when they meet one or more of the following criteria:

- Subject withdraws consent after being randomized (see Section 4.6)
- Subject is withdrawn after enrollment by investigator (see Section 4.8) including lost to follow-up

Completed

Subjects are considered completed when they are followed through Study Day 28 and complete the final study follow-up visit (Study Day 28) or die prior to this study visit.

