4.11 Emergency Unblinding

Any pregnancy occurring on study will be immediately unblinded (regardless of known AE or known fetal toxicities).

Any hospitalization occurring during treatment (Days 0-5 of this study) due to influenza symptoms will be unblinded, as knowing treatment may influence the subjects subsequent care (including choice of antivirals).

If AEs occur and investigators are concerned about the treatment allocation, the treatment can be discontinued as discussed in Section 4.8. However, if all of the following three criteria are met, the subject's randomization may be unblinded:

1. The AE must be a SAE as also defined in Section 8.2
2. The AE must be thought to be probably or definitely related to the study drug.
3. The treating clinician states that knowledge of the treatment arm may change the therapy provided to the patient.

The procedure for unblinding will be detailed further in the Manual of Operations (MOP).

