6.2 Hospitalization

Hospitalized subjects are excluded from this study. Subjects who initially are outpatients and are then hospitalized for influenza related symptoms should be unblinded to know the treatment obtained during this study and should receive antivirals as clinically indicated.

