8.4 Investigator Reporting Responsibilities to the Sponsor

8.4.1 Adverse Events

AEs that are to be recorded for this study (as noted above) will be fully and completely documented on the AE eCRF and in the subject’s clinical chart.

In the event that the subject is withdrawn from the study due to an AE, it must be recorded on the eCRF as such. The subject should be followed and treated by the Investigator until the adverse event has resolved or stabilized, even if this extends past the 28 day follow up period. It is up to the clinician to determine that the AE/SAE is resolved or has reached a stable state, after which no further follow-up is necessary. There should be documentation to support that determination.

Once an AE or SAE is known, research team members at the study site should ensure that subjects receive appropriate care. All actions taken by the Investigator after observing an AE or SAE should be documented, including increased monitoring of the subject, suspension of the treatment, etc.

Assessment of safety will include clinical observations and monitoring of hematological, blood chemistry, and immunologic parameters. The investigator must document all directly observed AEs and all spontaneously reported AEs. AEs will be documented on the AE eCRF in appropriate medical terminology. The severity and the relationship to the study intervention will be determined and reported on the eCRF.

Any intermittent or as needed use of any medication (specifically, any newly prescribed medication) during the course of the study may indicate the occurrence of an AE that may need to be recorded on both the AE eCRF and the concomitant medication form.

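### Protocol 4.8 lets a subject be withdrawn solely for an early hospitalization, although 4.7 already stops drug and keeps follow-up: a small, avoidable loss of outcome-related data

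*Protocol*

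**What the plan says.** Protocol 4.7 tells the investigator to stop study medication for four reasons, one of which is hospitalization within 5 days of enrollment. It then says what happens next: "All subjects who discontinue study drug will be encouraged to comply with the" visit schedule, clinical and virologic assessments included.

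Protocol 4.8 gives reasons for which a subject may be withdrawn from the study altogether. One is "Subject is hospitalized within 5 days of enrollment", in the same words as 4.7. The adverse-event bullet beside it applies only if the investigator believes that continuing would harm the subject, and it contrasts itself with 4.7. The hospitalization bullet carries neither condition.

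Protocol 3.2 counts as discontinued a subject who meets this description: "Subject is withdrawn after enrollment by investigator (see Section 4.8) including lost to follow-up". Enrolled status, which 3.2 defines for collecting data and samples and for reporting adverse events, ends at that point.

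Other provisions bear on the consequences:

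- Protocol 4.11: "Any hospitalization occurring during treatment (Days 0-5 of this study) due to influenza symptoms will be unblinded". Protocol 6.2 adds that such subjects "should receive antivirals as clinically indicated". It does not call for withdrawal.
- Protocol 4.6: "Subjects who indicate interest in withdrawing from the study should also be asked permission to be contacted at Day 28". This is addressed to subjects who themselves wish to leave.
- Protocol 4.8: "The investigator is to make every attempt to follow all serious adverse events (SAEs) to resolution". Protocol 8.4.1, for a subject withdrawn because of an adverse event: "The subject should be followed and treated by the Investigator until the adverse event has resolved or stabilized", past Day 28 if need be.

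**The concern.** One event has two possible consequences, and no rule chooses between them. Under 4.7 the subject stops drug and is encouraged to keep attending. Under 4.8 the investigator may end participation for the admission alone. Renal insufficiency and pregnancy, the other specific triggers in 4.7, are not carried into 4.8.

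Any loss through this route is tied to outcome, because only subjects who were admitted can be lost this way. For influenza-related admissions during treatment, the arm has been or should have been disclosed, so the decision to withdraw can be taken with the allocation known. A subject withdrawn by the investigator is also not covered by the Day 28 contact in 4.6.

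At stake are the Day 3 swab if the admission comes early, the Day 7 swab (which SAP 4.11 needs for resistance evaluation), the remaining diary entries, and complications or vital status after the SAE has resolved. Complications and 28-day mortality are listed secondary endpoints.

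**Working it through.** **1. The plan's own figure.** Protocol 9.2.1 gives 490 evaluable subjects, and 546 after 10% missing, for 42.5% versus 57.5% with 90% power and two-sided 0.05.

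- Per arm without continuity correction: n = [1.960 × √(2 × 0.5 × 0.5) + 1.2816 × √(0.425 × 0.575 + 0.575 × 0.425)]² / 0.15² = (1.386 + 0.896)² / 0.0225 = 231.4.
- With continuity correction: (231.4 / 4) × [1 + √(1 + 4 / (231.4 × 0.15))]² = 244.6, so 245 per arm and 490 in total.
- With 10% missing: 245 / 0.90 = 272.2, so 273 per arm and 546 in total. The stated figures reproduce.

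**2. The allowance for missing Day 3 results.** The main study has 510 subjects. Ten per cent is 51, which leaves 459 with a result. At 229.5 per arm the pooled normal approximation gives 89.8% power, in line with the protocol's approximately 90%. Protocol 9.2.1 names losses to follow-up among the causes that the 10% covers.

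**3. How many subjects could be affected.** No admission rate is given. Protocol 1.3.2 says only that all-cause hospitalization was very low in the two earlier adult trials. I assume 0.5% to 2% admitted within 5 days. The base is 510, since the 50 pilot subjects have finished and new wording cannot recover their data.

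| Assumed admission rate | Admitted, of 510 | Share of the 51 allowed for |
|---|---|---|
| 0.5% | 510 × 0.005 = 2.55 | 2.55 / 51 = 5% |
| 1% | 510 × 0.01 = 5.1 | 5.1 / 51 = 10% |
| 2% | 510 × 0.02 = 10.2 | 10.2 / 51 = 20% |

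These are ceilings. They take every admitted subject as withdrawn, although 4.8 says only that subjects may be. If a quarter were withdrawn (also assumed), the range would be 2.55 × 0.25 = 0.6 to 10.2 × 0.25 = 2.6 subjects. Subjects enrolled before a change in wording would not benefit either.

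**4. What is lost and what is already protected.**

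| Item | If withdrawn under 4.8 | Existing protection |
|---|---|---|
| The admission itself | Not lost; it has already occurred | SAP 4.6 analyses it |
| Course of the SAE | Followed | Protocol 4.8, 8.4.1, 8.6 |
| Day 3 swab | Lost only if the admission precedes it | SAP 4.8.1c: missing results set to best and worst cases |
| Diary data | Lost from withdrawal on | SAP 4.9a: best and worst cases |
| Day 7 swab | Lost | No missing-data sensitivity analysis in SAP 4.8.2 or 4.11 |
| New complication after the SAE resolves | May be missed | None in SAP 4.9f |
| Death after the SAE resolves | May be missed | SAP 4.6c censors at last contact |

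SAP 4.4 also tabulates losses with reasons and compares time to loss between arms, so the losses would be visible.

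**The case against.** The best defence is that the two sections do not contradict each other. Section 4.7 is mandatory and sets follow-up as the default, while 4.8 is permissive and sits under a general right of the investigator to withdraw subjects. Deleting one bullet leaves that right in place. This stands in part: the loss is possible, not certain. It does not justify offering admission alone as a sufficient reason, when the bullet beside it shows that the authors knew how to require a judgment of harm.

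A second defence is that the data have limited value. Subjects admitted for influenza may receive open-label antivirals, so later swabs and diaries partly reflect that treatment, and SAP 4.11 treats resistance as descriptive. This stands for virology. It does not apply to vital status and complications, which remain informative for a comparison of the arms as randomized.

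A third is that the unprotected remainder is thin. A death or pneumonia during the admission should be captured through SAE follow-up, and the earlier adult trials had no deaths. This stands, and it is why the point is rated at the lowest level. The absence of missing-data sensitivity analyses for mortality and complications applies to any dropout and is a separate matter from 4.8.

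A reader might also infer that the trial loses power. Removing 10.2 subjects from the 459 would lower the normal-approximation power from 89.8% to 89.1%. The documents do not support that step, because these losses belong to the 10% already deducted. Nor would every admitted subject miss the Day 3 swab: the criterion spans 5 days, and later admissions come after it.

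**Conclusion.** The point holds as a small defect of wording with a real, if rare, consequence. Protocol 4.8 permits an outcome-related withdrawal that 4.7 makes unnecessary. At most about 3 to 10 of 510 main-study subjects would be affected. That range rests on an assumed admission rate of 0.5% to 2% and on every admitted subject being withdrawn. Neither the sample size nor the stated power is in question.

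Two stronger readings should not be drawn. One is that up to 4.0% of an arm (10.2 / 255) could have unknown complications or vital status. That needs the highest assumed rate, withdrawal of everyone admitted, all of them in one arm, and no information from SAE follow-up, which the protocol requires. The other is that all such withdrawals would be made with the arm known. Protocol 4.11 and 6.2 provide for routine unblinding only when the admission is influenza-related; other admissions are unblinded only under the narrower conditions in 4.11.

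Cheap improvement, lowest severity.

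**What to change.** - Delete the hospitalization bullet from Protocol 4.8. Keep the bullet on adverse events where continuing would be detrimental, so that investigators retain discretion for a sick inpatient.
- State in Protocol 4.7 and 6.2 that hospitalized subjects stop study drug and remain in follow-up to Day 28 for vital status and complications, with swabs where feasible.
- Extend the Day 28 contact in Protocol 4.6 to subjects withdrawn by the investigator who have not fully withdrawn consent.

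The cost is one deleted bullet, a few sentences and a few extra contacts. Stopping drug, emergency unblinding, clinically indicated antivirals and the subject's right to leave are unchanged. The sample size stays at 560, and this change requires no amendment to the SAP. Swabs taken after admission should be read with the open-label antivirals in mind.

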4.9 Discontinuation of Study

The National Institute of Allergy and Infectious Diseases (NIAID), as the study sponsor, has the right to terminate this study at one or all sites at any time.

The reviewing IRB/IEC and any reviewing national regulatory agencies (if applicable) have the right to terminate the study at the sites it is responsible for at any time. Reasons for terminating the study may include, but are not limited to, the following:

- The incidence or severity of an AE in this or other studies indicates a potential health hazard to subjects
- Subject enrollment is unsatisfactory
- Data recording is inaccurate or incomplete
- Investigators do not adhere to the protocol or applicable regulatory guidelines in conducting the study

4.10 Participation in Other Protocols

Subjects in this protocol may participate in other research protocols, as long as the other research protocol(s) does not require more than 100 mL of blood to be given in any 4-week period of time that overlaps with this study, and does not administer any unlicensed drug, unlicensed vaccine,

or any investigational treatment for influenza within the 30 days or 5 half-lives (whichever is longer) prior to enrollment or during the duration of this study.

Note: The above may not represent the maximum amount of blood permitted to be collected by most IRBs/IECs. However, each site should ensure that these collection amounts are within the site's institutional and local limits.

4.11 Emergency Unblinding

Any pregnancy occurring on study will be immediately unblinded (regardless of known AE or known fetal toxicities).

Any hospitalization occurring during treatment (Days 0-5 of this study) due to influenza symptoms will be unblinded, as knowing treatment may influence the subjects subsequent care (including choice of antivirals).

If AEs occur and investigators are concerned about the treatment allocation, the treatment can be discontinued as discussed in Section 4.8. However, if all of the following three criteria are met, the subject's randomization may be unblinded:

1. The AE must be a SAE as also defined in Section 8.2
2. The AE must be thought to be probably or definitely related to the study drug.
3. The treating clinician states that knowledge of the treatment arm may change the therapy provided to the patient.

The procedure for unblinding will be detailed further in the Manual of Operations (MOP).

5 TREATMENT

Subjects will be randomized to one of the following two arms (Table 3):

Table 3: Treatment Allocation

| Arm | Drug | Allocation Ratio | Capsule |
|------------|----------------------------|-------------------------|--------------------|
| 1 | Oseltamivir | 1 | Oseltamivir |
| 2 | Oseltamivir placebo | 1 | Placebo |

5.1 Method of Assignment to Treatment

Subjects who meet all criteria for enrollment will be randomized using an interactive web-based system. A central randomization scheme will be prepared by the sponsor or designee.

Additionally randomization will be stratified based on duration of symptoms prior to randomization: (0–24 hours and 25–48 hours).

5.2 Study Regimens and Administration

Each randomized subject will receive a study drug kit consisting of 5 days of study capsules. Subjects take one capsule twice daily, and each dose will consist of the following:

- One of capsule A (Oseltamivir 75 mg)
Total dose: 150 mg/day for 5 days

OR

- One of capsule B (matching placebo)
Total dose: 2 placebo capsules/day for 5 days

The Division of Clinical Research, NIAID, NIH (the sponsor), will supply the oseltamivir and matching placebo for the study regimen.

The active capsule consists of commercial oseltamivir capsules over encapsulated with an opaque capsule. The placebo capsule consists of the identical opaque capsule filled with microcrystalline cellulose. Assembled treatment kits will be supplied to the participating sites.

Subjects should be instructed to take the study agent with food to avoid possible GI upset.

5.3 Justification of Dose

Oseltamivir: 75 mg bid is the standard licensed dose for the treatment of influenza.

5.4 Surveillance

During the conduct of this study the potential exists for the emergence of viruses resistant to oseltamivir. The protocol team will monitor the emergence of resistance to oseltamivir and current treatment recommendations. Should such a change occur where oseltamivir is no longer active for the majority of circulating strains (thus losing the ability to compare the two arms in the study), the study may be held or stopped.

5.5 Study Drug Acquisition

Study drug will be stored in a central repository. Sites will be given an initial supply of study drug after the local IRB/IEC has approved the study, all applicable national regulatory agencies have granted the study safe to proceed, the sponsor has approved shipment of study agent, and after all import licenses have been obtained, as applicable.

5.6 Study Drug Accountability

The investigator or his/her designee is required to maintain accurate drug accountability records. A binder containing instructions and the required accountability documentation will be provided to the investigator or his/her designee. When the study is completed, copies of the study drug accountability records will be maintained at the study site. Copies of the drug accountability records must be maintained with the rest of the documentation for the study. All unused study drug must be disposed of upon authorization by NIAID or its designee. All records regarding the disposition of study drug must be available for inspection by the study monitors and regulatory authorities.

5.7 Concomitant Medications

Subjects will be monitored throughout the study for use of concomitant medications. Any prescription medications, over-the-counter (OTC) preparations, herbal remedies, and/or nutritional supplements taken during the study period must be recorded on the source document and in the eCRF.

5.8 Prohibited Medications

Subjects may not receive investigational medications (other than the study drug provided) any time during the study. Their use would not be considered standard care, and therefore, withholding these compounds would still be consistent with best medical practice. This includes licensed drugs at non-approved doses, or drugs available under an Emergency Use Authorization (EUA).

5.9 Treatment Compliance

Treatment compliance will be assessed by examination of subject's remaining study product on each study visit. Subjects should be asked to bring the study kit to each study visit and returned to the study team on Day 7.

6 STUDY PROCEDURES

The following table (Table 4) outlines all of the assessments to be conducted during the study. A detailed presentation of assessments immediately follows the table. Total volumes of blood drawn are noted in the text for each study day. Details regarding the research samples (tubes, swabs, etc) will be detailed in the Manual of Procedures. The day when the subject is enrolled and randomized is denoted as Study Day 0, the first day after randomization is Study Day 1, etc.

Table 4: Schedule of Assessments

| Day +/- Window Evaluation/Procedure | Screen | Baseline | | | | | |
|--|---------------|-----------------|--------|--------|---|-------|--------|
| | -1 to 0 | 0 | 1 Home | 2 Home | 3 | 7 ± 1 | 28 ± 3 |
| ELIGIBILITY | | | | | | | |
| Informed consent | X | | | | | | |
| Demographics | X | | | | | | |
| Medical history | X | | | | | | |
| Site influenza testing (PCR or rapid Ag, See Section 7.2.2) | X | | | | | | |
| RANDOMIZATION/ STUDY DRUG | | | | | | | |
| Randomize subject | | X | | | | | |
| Dispense Study Treatment Kit | | X | | | | | |
| STUDY PROCEDURES | | | | | | | |
| Review and collect diary card (see Section 7.3.1) | | X ¹ | | | X | X | X |
| Assess for complications of influenza (see Section 7.3.2) | | X | | | X | X | X |
| Vital signs, including SaO ₂ (see Section 7.3.3) | X | X | | | X | X | X |
| Assessment of study drug compliance (see Section 7.5) | | | | | X | | |
| Review of concomitant medications | | | | | X | X | X |
| Physical exam ² (see Section 7.1.2) | X | | | | X | X | X |
| Adverse events | | | | | X | X | X |
| SAFETY LABORATORY | | | | | | | |
| Urine βHCG (for females of childbearing potential) | X | | | | | | |
| REFERENCE PROCEDURE | | | | | | | |
| Nasopharyngeal swab for virus isolation | | X | | | X | X | |
| Subject sample self-collection (see Section 6.3.3.2) | | X | X | X | X | | |
| Stored Serum | | X | | | X | X | X |

Notes: 1. On Day 0, subject will be instructed on how to complete the diary card, and baseline assessment will be collected.

2. Brief physical examinations will be conducted at screening to ensure there are not medical conditions (either chronic or acute) that would increase a subject's risk for participation in this study. Symptom-targeted physical examinations will be conducted at all other visits as needed to evaluate new complaints and possible adverse events.

